1.3.2. Rationale for Pharmacokinetic Sampling

The sampling schedule that follows the single dose of BGB-DXP593 is designed to capture data at a sufficient number of timepoints to provide a detailed profile of the concentration-time curve, including C_{max}, AUC from time zero to the time of the last quantifiable concentration (AUC_t), AUC from time zero to Day 29 (AUC₀₋₂₉), AUC_{inf}, time to maximum observed concentration (t_{max}), terminal half-life (t_{1/2}), clearance (CL), and volume of distribution (V_z).

Rich PK sampling will be performed in the first-in-human study in healthy subjects (Study BGB-DXP593-101). PK sampling in this study is limited to essential site visits to reduce patient burden.

1.3.3. Rationale for Biomarker Strategy

Biomarker analyses will be performed to evaluate study treatment effects induced in patients as well as to explore potential predictive biomarkers of response to BGB-DXP593.

Seroconversion for patients with COVID-19 usually happens within the first week after symptom onset (Wolfel et al 2020). It has been shown that seroconversion occurred after 7 days in 50% of patients and almost all COVID-19 patients had neutralizing antibodies within 1 month after symptom onset, thus the existing anti-SARS-CoV-2 antibodies in patients may have an impact on the efficacy of BGB-DXP593, which is also a neutralizing antibody for SARS-CoV-2. Therefore, the baseline SARS-CoV-2 serology antibody levels may be related to the treatment effects of BGB-DXP593. Recent studies have suggested that certain mutations on SARS-CoV-2 virus may impact the infectivity and severity of the virus, especially the mutations on the receptor binding domain of SARS-CoV-2, which may also impact the neutralizing activities of SARS-CoV-2 neutralizing antibodies (Baum et al 2020; Korber et al 2020; Li et al 2020). Thus, certain mutations on SARS-CoV-2 genome may also be related to the treatment effects of BGB-DXP593.

In addition, patients with COVID-19 have shown a strong upregulation of cytokine and interferon production, it is believed that dysregulated host immune response and production of inflammatory cytokines, known as the “cytokine storm”, correlates with disease severity and poor prognosis of SARS-CoV-2 infection (Tay et al 2020). Therefore, serum cytokine levels could be a marker for evaluating disease severity and the treatment effects of anti-SARS-CoV-2 neutralizing antibodies.

Considering the immune response induced by SARS-CoV-2 infection varies a lot among different patients, all patients may not be equally likely to benefit from treatment with anti-SARS-CoV-2 neutralizing antibodies. Predictive biomarker samples collected before dosing will be assessed in an effort to identify those patients with certain gene signatures who are most likely to respond to BGB-DXP593. Thus, gene signatures at baseline and after treatment in peripheral blood may serve as predictive biomarkers and may also help to explore the mechanism of response.

1.4. Benefit-Risk Assessment

On March 11, 2020, the Novel Coronavirus Disease, COVID-19, was declared a pandemic by the WHO. As of July 9, 2020, more than 12 million cases of COVID-19 have been reported globally, including more than 550,000 deaths. However, only remdesivir is approved for the treatment of severe COVID-19, and thus the unmet medical needs remain high.

Several studies showed that high viral load is associated with increased mortality. Seroconversion (detection of anti-SARS-CoV-2 IgM or IgG in blood) occurred in around 50% of patients 7 days after disease onset. Presence of anti-SARS-CoV-2 IgG is associated with viral load reduction (Bryan et al 2020; Fajnzylber et al 2020; Pujadas et al 2020; Wolfel et al 2020). With early administration of antiviral neutralizing antibodies, patients may benefit from early and rapid reduction of viral load and potential improved clinical outcomes.

BGB-DXP593 is a potent neutralizing antibody to SARS-CoV-2. It is human IgG type 1 selected from blood of convalescent patients. In preclinical studies, its pre- and post-exposure prophylactic effects to COVID-19 have been demonstrated. In a toxicological study in monkeys, no adverse events (AEs) were observed with repeated doses of BGB-DXP593 30-300 mg/kg.

As an exogenous protein, use of BGB-DXP593 might be related with hypersensitivity reactions, though the immunogenicity is considered low due to its human origin. Potential antibody-dependent enhancement (ADE) has been observed in some viral infections, such as Dengue fever. Possibility of ADE with passive immunity cannot be excluded in COVID-19. However, clinical experiences with RSV, influenza and dengue provide strong evidence that the circumstances that are proposed to lead to ADE of disease—including low affinity or cross-reactive antibodies with limited or no neutralizing activity or suboptimal titres—are very rarely implicated as the cause of severe viral infection in the human host (Arvin et al 2020). BGB-DXP593 is a highly potent neutralizing antibody, and thus is unlikely to cause ADE. In addition, a large number of COVID-19 patients have received convalescent plasma therapy, where no hints of ADE have been identified (Joyner et al 2020).

There are no FDA-approved treatments or accepted standardized medical treatment options indicated for mild to moderate COVID-19. Patients may benefit from the treatment of BGB-DXP593 based on its mechanism of action and the proven efficacy in COVID-19 animal models. BGB-DXP593 has a favorable preclinical safety profile. Patients enrolled in this clinical study will be closely monitored by means of reporting AEs, recording vital signs, and conducting clinical laboratory safety tests of blood and urine. The favorable preclinical safety profile, potential wide range application in the COVID-19 population and high unmet medical need provides substantive evidence that BGB-DXP593 has a favorable risk-benefit profile.

1.5. Study Conduct

This study will be conducted in compliance with the protocol approved by the Institutional Review Board (IRB) or Independent Ethics Committee (IEC) and in accordance with Good Clinical Practice (GCP) standards.

2. STUDY OBJECTIVES AND ENDPOINTS

2.1. Study Objectives

2.1.1. Primary Objective

- To evaluate the efficacy of BGB-DXP593 administered intravenously as a single dose in patients with mild to moderate COVID-19

2.1.2. Secondary Objectives

- To evaluate the safety of BGB-DXP593 administered intravenously as a single dose in patients with mild to moderate COVID-19
- To characterize the pharmacokinetic (PK) profile of BGB-DXP593 administered intravenously as a single dose in patients with mild to moderate COVID-19
- To evaluate the potential immunogenicity of BGB-DXP593 administered intravenously as a single dose in patients with mild to moderate COVID-19

2.1.3. Exploratory Objective

- 

2.2. Study Endpoints

2.2.1. Primary Endpoint

- Change from baseline to Day 8 in Severe Acute Respiratory Syndrome Coronavirus 2 (SARS-CoV-2) viral shedding as measured by reverse transcription-quantitative polymerase chain reaction (RT-qPCR) in nasopharyngeal swab samples

2.2.2. Secondary Endpoints

- Time-weighted average change in SARS-CoV-2 viral shedding as measured by RT-qPCR in nasopharyngeal swab samples from baseline to Day 15
- Change in SARS-CoV-2 viral shedding as measured by RT-qPCR in nasopharyngeal swab samples from baseline to Day 15
- Time to negative RT-qPCR in all tested samples with no subsequent positive RT-qPCR in any tested samples
- Proportion of patients requiring hospitalization due to worsened COVID-19
- Time to resolution of all COVID-19-related symptoms
- All-cause mortality rate at Day 29
- Incidence and severity of treatment-emergent adverse events (TEAEs) and serious adverse events (SAEs)

- PK parameters: maximum observed concentration (C_{max}), area under the concentration-time curve (AUC) from time zero to the time of the last quantifiable concentration (AUC_t), AUC from time zero to Day 29 (AUC_{0-29}), AUC from time zero to infinity (AUC_{inf}), time to maximum observed concentration (t_{max}), terminal half-life ($t_{1/2}$), clearance (CL), and volume of distribution (V_z) as appropriate
- Immunogenic responses to BGB-DXP593 evaluated through the detection of antidrug antibodies (ADAs)

2.2.3. Exploratory Endpoints

3. STUDY DESIGN

3.1. Summary of Study Design

This is a Phase 2, randomized, double-blind, placebo-controlled study to evaluate the efficacy and safety of BGB-DXP593 in patients with mild to moderate COVID-19.

[figure not shown]
The study will be conducted across approximately 20 to 30 sites internationally.

After providing written informed consent, completing all screening assessments, and being confirmed as eligible for study participation, patients will be randomized in a 1:1:1:1 ratio to receive placebo, BGB-DXP593 5 mg/kg, BGB-DXP593 15 mg/kg, or BGB-DXP593 30 mg/kg. Patient randomization will be stratified by country and disease severity (mild versus moderate COVID-19). The patients will receive a single intravenous infusion of placebo or BGB-DXP593 over 30 to 90 minutes. The patients will then be followed to Day 113 (± 7 days) to assess the efficacy, safety, PK, and immunogenicity. Nasopharyngeal swabs will be collected according to the Schedule of Assessments (Appendix 1) for RT-qPCR testing of SARS-CoV-2 to assess the change in viral load after study treatment. Approximately 172 patients will be randomized.

An Independent Data Monitoring Committee (IDMC) will periodically monitor safety and efficacy data. The first safety review is planned after at least 12 patients have been treated and followed up for 7 days.

The study schema is provided in Figure 2.

Figure 2: Study Schema

Note: Patients will be randomized based on stratification factors of country and disease severity (mild versus moderate COVID-19).

Patients will be monitored for safety, efficacy, PK, and immunogenicity during the study.

Assessments of safety will include AEs, SAEs, clinical laboratory tests, physical examinations, vital signs, and electrocardiograms (ECGs). AEs will be graded for severity according to the current version of the National Cancer Institute-Common Terminology Criteria for Adverse Events (NCI-CTCAE) Version 5.0. Refer to Section 9 for additional and specific information regarding AE monitoring and reporting.

RT-qPCR analysis will be used to assess the SARS-CoV-2 viral load in different samples at various timepoints, including nasopharyngeal swabs, saliva, and blood. The viral load in nasopharyngeal swabs will be used for primary efficacy analysis.

WHO 8-point ordinal scale will be used for clinical status assessment.

PK and ADA sampling will be conducted at timepoints specified in [Appendix 2](#).

Biomarker analysis will include, but are not limited to, SARS-CoV-2 mutations, serology, cytokines, and gene expression signatures.

Study procedures and assessments are further detailed in [Section 7](#) and [Section 8](#), respectively, and the Schedule of Assessments can be found in [Appendix 1](#).

4. STUDY POPULATION

The specific eligibility criteria for selection of patients are provided in Section 4.1 and Section 4.2. The sponsor will not grant any eligibility waivers.

4.1. Inclusion Criteria

Each patient must meet all of the following inclusion criteria to be considered eligible for participation in this study:

1. Participant must be at least 18 years of age at the time of signing the informed consent.
2. Laboratory-confirmed SARS-CoV-2 infection (positive reverse transcription-polymerase chain reaction [RT-PCR] test or other testing methods authorized by local regulatory authorities) in any samples following local practice ≤ 72 hours prior to screening
3. Have experienced COVID-19 symptoms for ≤ 7 days prior to treatment assignment, such as fever, cough, shortness of breath, sore throat, diarrhea, vomiting, and dysgeusia
4. Agree to the collection of nasopharyngeal swabs, saliva, and venous blood
5. Female patients of childbearing potential must be willing to use a highly effective method of birth control (see [Appendix 4](#)) from the time of study enrollment until 4 months after the study dosing
6. Male patients with female partners of childbearing potential must be willing to use a highly effective method of birth control (see [Appendix 4](#)) from the time of study enrollment until 4 months after the study dosing
7. Able to provide written informed consent and can understand and agree to comply with the requirements of the study and the schedule of assessments

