7.1. Screening Period

Screening evaluations will be performed within 3 days before the study drug administration. A patient who agrees to participate in this study will sign the informed consent form (ICF) before undergoing any study-specific procedures. Refer to [Section 8.1](#) for instructions regarding screening assessments. Rescreening is not allowed. If the site is able to complete all the screening procedures, randomization, and study treatment in 1 day, the screening assessments can be combined with the Day 1 assessments.

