8.1.2. Review of SARS-CoV-2 Test Result

At screening, the investigator should review the positive results of SARS-CoV-2 test (RT-PCR or other tests authorized by local regulatory authorities) to confirm eligibility.

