8.3. Efficacy Assessment

8.3.1. Viral Load

The nasopharyngeal swab, saliva, and blood samples will be collected at the timepoints shown in [Appendix 1](#). The samples will be tested by the method of RT-qPCR in a central laboratory for the quantitative detection of nucleic acid from SARS-CoV-2.

To obtain nasopharyngeal swab samples, insert minitip swab with a flexible shaft (wire or plastic) through the nostril parallel to the palate (not upwards) until resistance is encountered or the distance is equivalent to that from the ear to the nostril of the patient, indicating contact with the nasopharynx. Swab should reach depth equal to distance from nostrils to outer opening of the ear. Gently rub and roll the swab. Leave swab in place for several seconds to absorb secretions. Slowly remove swab while rotating it. Specimens can be collected from both sides using the same swab, but it is not necessary to collect specimens from both sides if the minitip is saturated with fluid from the first collection. If a deviated septum or blockage create difficulty in obtaining the specimen from one nostril, use the same swab to obtain the specimen from the other nostril.

The process to collect saliva samples is defined in the laboratory manual.

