6 STATISTICAL METHODS

6.1 ANALYSIS SETS

- The Intent-to-Treat (ITT) Analysis Set includes all randomized patients. Patients will be analyzed according to the treatment assigned at randomization. This will be the primary analysis set for efficacy analyses.
- The Safety Analysis Set includes all patients who have received the study drug (BGB-DXP593 or placebo). Patients will be analyzed according to their actual treatment received. The Safety Analysis Set will be used for all safety analyses.
- The PK Analysis Set includes all patients who received the study drug (BGB-DXP593) per the protocol and for whom any postdose PK data are available.
- The ADA Analysis Set includes all the patients who received the study drug and in whom both baseline ADA and at least 1 postbaseline ADA results are available.

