6.2 DATA ANALYSIS GENERAL CONSIDERATIONS

6.2.1 Definitions and Computations

Study day is calculated in reference to the date of randomization. For assessments conducted on or after the date of randomization, study day will be calculated as assessment date – date of randomization + 1. For assessments conducted before the date of randomization, study day is calculated as assessment date – date of randomization. There is no study day 0.

In the situation where the event date is partial or missing, the date will appear partial or missing in the listings. Study day and any corresponding durations will be presented based on the imputations specified in Appendix 10.1.

Baseline is defined as the last non-missing value collected before the administration of the study drug.

All calculations and analyses will be conducted using SAS version 9.4 or higher.

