6.2.2 Conventions

Unless otherwise specified, the following conventions will be applied to all analyses:

- 1 year = 365.25 days. Number of years is calculated as (days/365.25) rounded up to 1 decimal place.
- 1 month = 30.4375 days. Number of months is calculated as (days/30.4375) rounded up to 1 decimal place.
- Age will be calculated as the integer part of (date of informed consent – date of birth + 1)/365.25
- P-values will be rounded to 4 decimal places. P-values that round to 0.0000 will be presented as '< 0.0001' and p-values that round to 1.000 will be presented as '> 0.9999'.
- Time-to-event or duration of event endpoints will be based on the actual date the test was obtained rather than the associated visit date.
- Missing efficacy or safety data will not be imputed unless otherwise specified.
- For laboratory results collected as > x, the value of the laboratory results will be set as x. For laboratory results collected as < x, the value of the laboratory results will be set as x divided by 2.
- For by-visit observed data analyses, percentages will be calculated based on the number of patients with non-missing data as the denominator, unless otherwise specified.
- Unscheduled measurements and retested measurements will not be included in by-visit table summaries and graphs but will contribute to the best/ worst case value where required (e.g. shift table). Listings will include scheduled, unscheduled and retest data.
- For continuous endpoints, summary statistics will include n, mean, standard deviation, median, Q1, Q3 and range (minimum and maximum).

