6.4.2 Secondary Endpoint Analyses

Secondary efficacy endpoints will include:

- Time-weighted average change in viral shedding as measured by RT-qPCR in nasopharyngeal swab samples from baseline to Day 15
- Change in SARS-CoV-2 viral shedding as measured by RT-qPCR in nasopharyngeal swab samples from baseline to Day 15
- Time to negative RT-qPCR in all tested samples with no subsequent positive RT-qPCR in any tested samples
- Proportion of patients requiring hospitalization due to worsened COVID-19
- Time to resolution of all COVID-19-related symptoms
- All-cause mortality rate at Day 29

The time-weighted average change in viral shedding as measured by RT-qPCR in nasopharyngeal swab samples from baseline to Day 15 is defined as:

$$\frac{\sum_{i=a}^{b-1} [0.5 \times (Y_i + Y_{i+1}) \times (t_{i+1} - t_i)]}{t_b - t_a}$$

where Y_i is the change from baseline in viral shedding at Visit i , t is the time at the specified timepoint (the actual study day), a is the baseline assessment at Day 1, and b is the last assessment at or prior to Day 15 visit. Analysis of covariance (ANCOVA) model with corresponding baseline viral shedding, disease severity at baseline, and treatment as covariates will be used. Comparisons of active doses to placebo (90% CIs and p-values) will be provided.

The same MMRM analysis for primary endpoint will be used to analyze the change in SARS-CoV-2 viral shedding from baseline to Day 3 and Day 15. Comparisons of active doses to placebo (90% CIs and p-values) will be provided.

[figure not shown]
The negative RT-qPCR is defined as the value that is below the lower limit of detection. Kaplan-Meier method will be used to assess the time to negative RT-qPCR. The corresponding quartiles (including the median) will be reported and a two-sided 90% CI of median, if estimable, will be constructed with a generalized Brookmeyer and Crowley method for each dosing group. Patients who have died prior to experiencing the event of interest will be censored on the day of data cutoff. Patients for whom the RT-qPCR value is still positive by the time of end of study visit or data cutoff, whichever comes first, will be censored on the last RT-qPCR sample date.

[figure not shown]
The number of patients who require hospitalization due to worsened COVID-19 will be counted. Corresponding proportion will be derived and a two-sided binomial exact 90% CI of proportion will be constructed.

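### Time to negative RT-qPCR has no baseline-positive risk set, so patients with no detectable virus at baseline can pull the per-arm clearance estimates early

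*Protocol*

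**What the plan says.** **Entry.** Protocol 4.1 accepts a positive RT-PCR or another locally authorised test, "in any samples following local practice", no more than 72 hours before screening. Protocol 7.1 adds: "Screening evaluations will be performed within 3 days before the study drug administration". At screening, under Protocol 8.1.2, "the investigator should review the positive results of SARS-CoV-2 test". No central result is needed to enrol.

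**Endpoint measurement.** Nasopharyngeal swab, saliva and blood are collected before dosing and during follow-up. Protocol 8.3.1 states: "The samples will be tested by the method of RT-qPCR in a central laboratory".

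**Analysis set and baseline.** SAP 6.1: "The Intent-to-Treat (ITT) Analysis Set includes all randomized patients"; this is the primary set for efficacy. SAP 6.2.1: "Baseline is defined as the last non-missing value collected before the administration of the study drug". Neither sentence asks for a detectable value.

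**Time to negative.** The endpoint in SAP 6.4.2 is "Time to negative RT-qPCR in all tested samples with no subsequent positive RT-qPCR in any tested samples", where negative means below the lower limit of detection. It is summarised by Kaplan-Meier quartiles with a 90% CI for the median in each dosing group. SAP Table 1 dates the event at its occurrence, or at the first occurrence if there are several. No clock start is given for this endpoint, whereas time to symptom resolution runs from randomisation.

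**Primary endpoint.** The MMRM for change to Day 8 has baseline viral shedding and a visit-by-baseline term. The target-dose rule in SAP 6.4.1 uses a target effect of -1 log10 copies/mL.

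**The concern.** A patient who has no detectable virus in any tested baseline sample, and stays that way, cannot become negative. Such a patient belongs outside the risk set for clearance. The plan gives no rule for this case. Read literally, the all-randomised set and the first-occurrence rule record an event on Day 1, or at the first post-dose sample if predose results are not counted. Either way the event reflects the state at entry, not clearance under treatment.

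The effect is to move the curves and medians early in every arm and to narrow the visible gap between arms. These are descriptive secondary results, but readers will take them as the time patients need to clear the virus.

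A related, smaller matter concerns the primary endpoint. A patient with an undetectable baseline swab has almost no room to fall by Day 8, so the average effect compared with the -1 log10 target may be smaller than the effect in patients who had virus to clear.

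**Working it through.** **1. Can it happen?** The entry test may be 72 hours before screening, and screening may be 3 days before dosing: 3 + 3 = about 6 days between the qualifying test and the baseline samples. The qualifying test may also be a different method on a different sample from the central assay. Symptoms may have lasted up to 7 days. Protocol 1.3 says that around half of patients have detectable antibody by then and that high viral loads were rare after seroconversion. Only a history of positive serology excludes; the Day 1 serology sample is not used for eligibility. So an undetectable central baseline is possible. Its frequency is not in the documents.

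**2. When would it count as an event?** If all tested samples means swab, saliva and blood together, a negative swab alone is not enough. Protocol 1.3 also says that most patients have no viremia and that saliva tracks the swab well, so patients negative in all three are credible, though fewer than those with a negative swab.

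**3. Effect on the Kaplan-Meier curve.** Let q be the share negative in all baseline samples and staying so, and S0(t) the curve for the rest. The observed curve is S(t) = (1 - q) x S0(t) from the first post-dose sample on. With the same q in both arms, the gap between two arms at any visit shrinks by the factor (1 - q).

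Illustration, with assumed inputs: exponential clearance with a 10-day median, so S0(t) = 2^(-t/10), and q of 5%, 10% or 20%. The schedule, as its table reads, places post-dose swabs on Days 3, 8 and 15, that is t = 2, 7 and 14 days after Day 1. The expected share recorded as negative is 1 - (1 - q) x 2^(-t/10):

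| q | Day 3 | Day 8 | Day 15 | Median falls at |
|---|---|---|---|---|
| 0 | 12.9% | 38.4% | 62.1% | Day 15 |
| 5% | 17.3% | 41.5% | 64.0% | Day 15 |
| 10% | 21.7% | 44.6% | 65.9% | Day 15 |
| 20% | 30.4% | 50.8% | 69.7% | Day 8 |

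The median changes when (1 - q) x 2^(-0.7) reaches 0.5: q = 1 - 0.5/0.6156 = 18.8%. It moves in a step, give or take the 1-day visit window, while the curve itself is early at every q above zero.

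**4. Primary endpoint, as context.** Plan inputs: 41 per arm, one-sided 5%, maximum effect -1.5, SD 3.2, five candidate shapes; stated power at least 82%. A simulation of the multiple contrast test (critical value about 1.94) gives 82% for sigEmax, 72% for each Emax shape, and 70% for quadratic and linear; the mean is 73%. The stated figure is thus reproduced for one shape only.

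Now let q be the share with an undetectable baseline swab. Assume that these patients show no effect and that -1.5 applies to the others. The effect becomes -1.5 x (1 - q):

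| q | Effect | Linear power, SD 3.2 | Mean power, SD 3.2 | Mean power, SD x sqrt(1 - q) |
|---|---|---|---|---|
| 0 | -1.50 | 70% | 73% | 73% |
| 5% | -1.43 | 66% | 69% | 71% |
| 10% | -1.35 | 62% | 65% | 69% |
| 20% | -1.20 | 53% | 57% | 65% |

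**5. Against the -1 target.** Scaling the plan's shapes to -1.5 at 30 mg/kg (an assumption), Emax1 (ED50 2.6) predicts 1.5 x (5/7.6)/(30/32.6) = 1.07 at 5 mg/kg. The predicted effect falls short of 1 once q exceeds 1 - 1/1.072 = about 7%. Emax2 (ED50 12.5) predicts 1.5 x (15/27.5)/(30/42.5) = 1.16 at 15 mg/kg and falls short above 1 - 1/1.159 = about 14%. This shows only that the effect part of the rule can be sensitive to the baseline mix. It says nothing about which dose is suitable.

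**The case against.** - **The plan nowhere says that a predose negative is an event.** This stands. The point is a missing rule and a default reading. If saliva and blood count, only patients negative in every tested sample are affected.
- **No treatment comparison rests on this endpoint.** It is summarised per arm with no planned between-arm test, and the shift goes the same way in all arms. This stands and limits the consequence to the reported curves and medians.
- **The entry rules already favour patients with virus.** Symptoms are at most 7 days old, earlier positive tests and a positive serology history exclude, and screening and dosing may fall on one day. These lower the share but do not make it zero.
- **The power loss is conditional.** The share is assumed. The -1.5 planning effect is not tied to baseline-detectable patients, so scaling it may count the dilution twice. If the SD shrinks as well, the loss at 5% or 10% is small. All of this stands.
- **A supportive analysis may already be planned.** SAP 6.4.3 and 6.4.4 show headings only, and SAP 6.3.3 lists a baseline nasopharyngeal viral load group. It cannot be called absent.

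Baseline adjustment in the MMRM answers less. It reduces noise, but without a treatment-by-baseline term it still estimates one average effect across patients with and without virus to clear.

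**Conclusion.** The point holds as a cheap improvement to one secondary endpoint. Patients with no detectable virus in any tested baseline sample stay in the time-to-negative analysis although they are not at risk, and the default dating rule gives those who stay negative an event at or just after baseline. The direction is known: early, in each arm. The size is not, because the share is not given. Under the assumed 10-day exponential median, the observed median is unchanged at 5% or 10% and moves from Day 15 to Day 8 at about 19% or more.

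Three stronger readings do not follow from the documents:

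- That every patient with an undetectable baseline swab is counted as an event at baseline. The definition asks for all tested samples, and no text makes a predose negative an event.
- That the clearance median shrinks smoothly by a calculable number of days. Sampling on a few days rules that out.
- That the primary analysis is wrong or has a known loss of power. The all-randomised estimate is a legitimate one, and the power figures rest on an assumed share, an assumed zero effect and a choice about the SD.

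**What to change.** In SAP 6.4.2, for time to negative RT-qPCR:

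- limit the risk set to randomised patients with at least one detectable central RT-qPCR sample at baseline;
- count only post-dose negatives as events;
- state the clock start, and say whether all tested samples covers swab, saliva and blood together;
- report by arm how many patients are left out for lack of a detectable baseline sample.

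The baseline samples are taken before dosing, so the restriction keeps the randomised comparison intact.

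Keep ITT for the primary analysis. If the text of SAP 6.4.3 or 6.4.4 does not already provide it, add one supportive repeat of the MMRM and MCPMod analysis in patients with a detectable central nasopharyngeal baseline, read beside the ITT result and the -1 log10 target. This leaves the primary result as it is and shows whether that result depends on the baseline mix.

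Cost: a few sentences in the SAP and one repeat run. The restricted analyses lose a few patients, including any who are negative at baseline and turn positive later.
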